7.1. Research Method

Quantitative

7.2 Types of study

Prospective, observational, cross-sectional

7.3 Study Population:

All adults in the intensive care unit admitted with the diagnosis of Traumatic brain injury, SAH and acute stroke under treatment with IV 20% Mannitol.

7.4 Study site and its justification: Intensive care unit of TUTH, IOM.

Optic nerve sheath diameter has been used for the evaluation of patients with neurological lesion or injuries and in acute care settings. However no studies have been performed on its usefulness in our institute. It can be used to guide the treatment of acute episodes of raised intracranial pressure in the intensive care units and to quantify the efficacy of measures taken to reduce raised intracranial pressure. The examination is easy and is non-interventional, so examination can be made mandatory in such cases.

7.5 Sampling Method

Probability sampling

7.6 Sample size

Basis and method of determination including power of the study, level of significance etc.

Power of study: 80% ($1-\beta = 0.84$)

Level of significance: 95% ($\alpha = 0.05$)

Assuming mean difference and standard deviation of differences (σ) of 0.24 and 0.49 respectively, effect size (Δ) was 0.49 as derived from previous study²³,

Using the formula

$$N = \frac{(z_{1-\alpha/2} + z_{1-\beta})^2}{\Delta^2} + \frac{z_{1-\alpha/2}^2}{2},$$

The sample size required would be 35.

Assuming a dropout of 10%, the required sample size would be 40.

7.7 Inclusion and Exclusion Criteria

Inclusion criteria:

- Age > 18 yrs
- Gender: any
- H/o traumatic brain injury/ subarachnoid hemorrhage/ acute stroke
- Mean optic nerve sheath diameter > 5mm (0.5cm)
- Under osmotherapy with 20% Mannitol.

Exclusion criteria:

- Baseline ocular pathology like tumors, Grave's disease and Sarcoidosis
- Previous ocular surgery
- Decompressive cranial surgery

7.8 Study Variables:

Epidemiological variables:

- Age
- Gender
- Weight
- BMI

Measured base line variables:

- GCS score
- Mean arterial pressure
- Optic nerve sheath diameter, T₁ (mean of 3 measurements in each eye)
- Ventilator parameters (PIP and PEEP) in patients on mechanical ventilation.

Measured variables after infusion of 20% Mannitol:

- Dose of 20% mannitol administered
- Mean arterial pressure
- Optic nerve sheath diameter (mean of 3 measurements in each eye) after 30mins(T₂), 60 mins(T₃) and 120 mins(T₄).

7.9 Primary outcomes:

Change in the optic nerve sheath diameter (Δ ONSD) at T₂, T₃ and T₄.

7.10 Secondary outcomes:

- Change in the mean arterial pressure before and after mannitol administration.
- Comparison and correlation between the extent of change in ONSD (Δ ONSD) with dose of mannitol and change in MAP(Δ MAP).
- Correlation between Δ ONSD with PIP and PEEP in mechanically ventilated patients

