The incidence of elevated ICP is more than 50% in patients with ICP ranging as high as 80% in patients with traumatic brain injury.^{10, 11} The fundamental goal of management in TBI is based on managing ICP, maintaining adequate CPP and is based upon the Monro-Kellie doctrine and cerebral autoregulation.¹¹ Similarly incidence of raised intracranial pressure in patient with intracranial hemorrhage ranges from 36% to 80%.¹² Malignant cerebral edema leading to raised intra-cranial pressure is a major cause of adverse outcome in patients with acute ischemic stroke with an incidence of 10-20%. Use of osmotic therapy in such patients has been recommended in both ENLS guidelines for management of intra-cerebral hemorrhage and AHA/ASA guidelines.¹³

Mannitol, is a polyol (sugar and alcohol) a hyper-osmolar agent that has been used for osmotherapy in neurosurgical patients since many years. The proposed mechanism of its action are transient hypervolemia thus decreasing blood viscosity, increase in CBF and the microvascular circulation leading to autoregulatory vasoconstriction and thus reducing cerebral blood volume.¹⁴ However there is controversy regarding its mechanism of effect when given as single bolus dose. Its effect in red blood cell rheology and improved oxygen delivery/circulation has also been hypothesized for explaining its immediate effect in decreasing ICP¹⁴. Another hypothesis argues about the ability of Mannitol to lower intracranial pressure by reducing brain water content (diuretic effect)⁹ and decreasing CSF production.

Pharmacokinetics of Mannitol:

Onset of action: 15 minutes

Half life: 100 minutes

Osmolarity: 1100 for 20% Mannitol

Duration of action: 3-6 hours

Excretion: Urine (80%)

Time of peak action: 30- 100 minutes

Literature review:

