7.10 Expected Duration of the Study: 6 months

7.11 Tools and techniques for data collection:

Tools:

- 6-10 Hz linear array USG probe (Sonosite M-Turbo)
- Ultrasound coupling jelly
- Transparent dressing (Tegaderm)
- Cleaning gauze pieces
- Proforma
- Arterial blood pressure monitor (invasive or non-invasive)

Methodology:

- Included patients will be those above 18 years, admitted in the ICU of TUTH, Maharajgunj, with the diagnosis of traumatic brain injury, acute stroke or intracranial hemorrhage and under osmotherapy with 20% Mannitol.
- Written informed consent will be taken from the patient or patient's responsible guardian. Conscious patients will be explained about the procedure.
- The patient's diagnosis, epidemiological variables and baseline variables will be recorded.
- Baseline ventilator parameters will be noted and the ICU staffs instructed not to change those variables over the study period until deemed necessary by the treating physician.
- Positioning of the patient will be done: supine, 30° head elevated.
- Mean arterial blood pressure will be noted from arterial line readings or NIBP reading as appropriate or available.
- A protective transparent dressing will be placed over the closed eyelid in sedated or ventilated patients as an additional measure to prevent any irritation of the conjunctiva.
- For ONSD measurement, generous amount of coupling gel will be applied over the closed upper eyelid.
- The probe will be held with a pincer grasp between the thumb and index finger, using the remaining fingers for stability by resting them on the maxilla or supraorbital ridge.
- The depth will be adjusted to optimize the visualization of the intended structures, i.e. the optic nerve, the surrounding CSF space and the ONS. The gain will be adjusted to create a hypoechoic posterior chamber.
- The mechanical index will be adjusted as per the recommended values for the eye, in order to limit the amount of energy absorbed by the eye.
- Values will be noted 0.3 cm posterior to the retinal surface after optimal visualization of the entry of optic nerve in the orbit.

- Mean will be obtained after taking 3 readings in each eye. Only patients with mean ONSD > 0.5cm will be included and the baseline value designated as T₁.
- Intravenous 20% Mannitol as prescribed will be administered via a dedicated IV line over 20 minutes.

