- Mean arterial pressure and Optic nerve sheath diameter readings will be performed as previously described and noted at 30(T₂), 60(T₃) and 120(T₄) minutes after completion of IV administration.
- The coupling gel will be removed gently after each measurement and the protective adhesive dressing will be removed at the end of the study.

[figure not shown]
7.12 Management protocol of patients/participants if applicable:

All patients will be managed according to the current ICU protocol abiding with the ENLS and Brain Trauma Foundation guidelines for TBI and intra-cerebral hemorrhage and AHA/ASA guidelines for acute ischemic stroke. In subjects with persistently elevated intracranial pressure and ONSD findings above 5.0 mm despite the administration of 20% Mannitol, decision for further treatment will rest upon the treating physician.

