Research results will also be submitted for publication in national and international journals of repute.

14. Plan for Utilization of the Research Findings:

The research results would help us in the care of patients in the neurosurgical and neurological intensive care units with non-invasive monitoring.

15. Work Plan

S.N	Activities	2018 AD		2019 AD			
		Nov	Dec	Jan	Feb	Mar	Apr
1	Problem identification						
2	Literature review						
3	Topic selection						
4	Writing thesis proposal						
5	Presentation to sub committee						
6	Review thesis proposal						
7	Submission to IRB						
8	Approval from IRB						
9	Data collection						
10	Data analysis						
11	Final thesis writing						
12	Final correction and submission						

16. Ethical Consideration

Research is based on human optic nerve sheath diameter.

Approval by IRB.

Verbal consent from patients relatives and/or legal guardian would suffice as the study is non-interventional and non-invasive with no effect on patients safety.

Confidentiality will be maintained.

17. Obtaining the Consent

Patients legal guardian will be well counseled and no information will be withheld.

18. Budget

The expenditure during the study will be made by the principal investigator.

Transparent dressing (Tegaderm): 50 pcs: Rs. 2400

Data statistician: Rs. 8000

Stationary: Rs. 4000

Photocopies of proforma and information sheet: Rs.2000

Binding: Rs. 4000

Total: Rs 20400

19. Annexes:

Proforma

“Study on the effect of intravenous administration of 20% Mannitol on the Optic nerve sheath diameter (ONSD) in patients with episodes of raised intracranial pressure.”

Participant serial no.: IP no.: Date:

Name: Age/sex: Weight:

Height: BMI:

Diagnosis: Admission date:

Ventilator parameters at time of baseline measurement

PIP: cmH₂O
PEEP: cmH₂O

Time of 20% Mannitol administration:
Dose of 20% Mannitol administered:
Time of measurement: 30 minutes:
60 minutes:
120 minutes:

MEASURED VARIABLES:

VARIABLES	BASELINE (T ₁)	POST-MANNITOL (30MINUTES: T ₂)	60 MINUTE (T ₃)	120 MINUTES (T ₄)
MEAN ARTERIAL PRESSURE	mmHg	mmHg	mmHg	mmHg
OPTIC NERVE SHEATH DIAMETER	RIGHT: mm	RIGHT: mm	RIGHT: mm	RIGHT: mm
	LEFT: mm	LEFT: mm	LEFT: mm	LEFT: mm
	MEAN: mm	MEAN: mm	MEAN: mm	MEAN: mm
GLASGOW COMA SCALE	E:	E:	E:	E:
	V:	V:	V:	V:
	M:	M:	M:	M:

List of Abbreviations:

ICP	Intracranial pressure
TBI	Traumatic brain injury
SAH	Subarachnoid hemorrhage
ONSD	Optic nerve sheath diameter
CPP	Cerebral perfusion pressure
CBF	Cerebral Blood Flow

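### Patients can enter with an earlier mannitol dose still acting at T1, and no dose history is recorded, so the ONSD change may be biased by an amount that differs across T2, T3 and T4

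*Combined protocol and SAP*

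**What the plan says.** Section 7.3 defines the population as intensive-care adults with one of the listed diagnoses who are "under treatment with IV 20% Mannitol". Section 7.7 lists "Under osmotherapy with 20% Mannitol" as an inclusion criterion, and the methodology in 7.11 repeats it. The exclusions concern ocular pathology, ocular surgery and decompressive surgery; earlier osmotherapy is not among them.

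Section 7.11 then gives the sequence. Three readings per eye are averaged: "Only patients with mean ONSD > 0.5cm will be included and the baseline value designated as T₁". Next, "Intravenous 20% Mannitol as prescribed will be administered via a dedicated IV line over 20 minutes". MAP and ONSD are then "noted at 30(T₂), 60(T₃) and 120(T₄) minutes after completion of IV administration".

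The pharmacokinetics list in Section 3 gives "Duration of action: 3-6 hours", a half-life of 100 minutes and a peak at 30 to 100 minutes. The proforma in Section 19 has a single field for "Time of 20% Mannitol administration" and a single dose field. The primary outcome (7.9) is the change in ONSD at T2, T3 and T4. A secondary outcome (7.10) relates that change to dose. Section 7.13 plans paired t and chi-square tests, and Section 9 acknowledges that there is no control group.

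**The concern.** The plan treats T1 as the level from which the mannitol effect is measured. For a patient on repeat dosing, T1 may already be lowered by an earlier dose. As that dose fades or builds up over the following two hours, its own movement is added to the movement caused by the observed infusion. The paired difference cannot separate the two, and there is no comparison group to show the background drift.

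Two stated aims are exposed. The rationale (Section 4) is to describe the pattern and extent of change, and a bias that differs by time point alters the pattern itself. The dose correlation relates the change to the observed dose alone, so any earlier dose goes uncounted. Because dose history is not collected, first-dose and repeat-dose patients could not be told apart afterwards.

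**Working it through.** **The plan's own figure.** Section 7.6 uses a mean difference of 0.24 and an SD of differences of 0.49, so the effect size is 0.24/0.49 = 0.49. Then (1.96 + 0.84)²/0.49² + 1.96²/2 = 34.57, rounded up to 35, as stated. Exact paired-t power at n = 35 is 80.4%.

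**Timing.** The infusion takes 20 minutes and readings are timed from its completion. T2, T3 and T4 therefore fall at least 50, 80 and 140 minutes after T1.

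**Carry-over from a dose that is wearing off.** Inputs from Section 3: half-life 100 minutes, so k = ln 2/100 per minute. Assumptions not in the documents: the ONSD effect follows the plasma half-life, doses add, and one equal dose was given τ = 180 to 360 minutes before T1. The documents give no dosing interval; 3 to 6 hours is borrowed from the duration of action as an illustrative range.

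- Fraction of the earlier effect left at T1: exp(−kτ) = 0.287 at 3 h and 0.082 at 6 h.
- Part of that residual lost by t minutes after completion: 1 − exp(−k(t + 20)).
- Effect of the observed dose remaining at that time, counted from mid-infusion: exp(−k(t + 10)).
- Understatement = residual × part lost ÷ effect remaining.

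| Reading | Part of residual lost | Effect remaining | Dose 3 h before T1 | Dose 6 h before T1 |
|---|---|---|---|---|
| T2 | 0.293 | 0.758 | 11% | 3% |
| T3 | 0.426 | 0.616 | 20% | 6% |
| T4 | 0.621 | 0.406 | 44% | 13% |

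Example, T4 at 3 h: 0.287 × 0.621/0.406 = 0.44. With regular repeat doses the residual becomes r/(1 − r), which is 0.403 or 0.090, and the T4 figures are 62% and 14%.

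**On the planning scale.** Take 0.24 both as the earlier dose's peak effect and as the true change at every reading. If every patient had a dose 3 h before T1, the losses are 0.24 × 0.287 × (0.293, 0.426, 0.621) = 0.020, 0.029 and 0.043. The measured changes are then 0.220, 0.211 and 0.197, and power at n = 35 is 73%, 70% and 64%. For a dose 6 h before T1 the T4 loss is 0.012 and power is 76%. The T4 loss of 0.043 is 18% of 0.24, while the table shows 44%, because the table divides by the smaller effect remaining at T4.

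**Allowing for a rise to peak.** The calculation above has no rising phase. With a one-compartment rise-and-fall curve and the same half-life (positive = understated, negative = overstated, as % of peak effect):

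| Peak time | Earlier dose before T1 | T2 | T3 | T4 |
|---|---|---|---|---|
| 100 min | 30 min | −37 | −39 | −24 |
| 100 min | 60 min | −10 | −4 | +15 |
| 30 min | 30 min | +24 | +38 | +59 |

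With a peak at 30 minutes the change is understated at all three readings for every interval tried. For doses 3 and 6 h before T1 the conclusion at T4 is stable: with peaks at 30, 65 or 100 minutes, understatement is 44-45% and 13-19% of the effect remaining.

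**The case against.** T1 is a proper pre-dose baseline: it is measured just before the observed infusion. The objectives in Section 5 ask how ONSD changes after mannitol, and the proforma title speaks of episodes of raised pressure. The change after a dose as given in routine care is a legitimate observational target. That stands, and the full-set analysis should be kept. It does not answer the mixing of first-dose and repeat-dose patients in the time pattern and the dose correlation.

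A reader might infer that the ONSD change is understated as a matter of fact. The documents do not support that. It requires patients who were already dosed, a dose past its peak at T1, and nothing pulling the other way. A dose still rising can reverse the sign. The reading used for entry also serves as T1, so regression to the mean from the 5 mm threshold exaggerates the fall in an uncontrolled study.

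A reader might also infer that the threshold selects poor responders to the earlier dose. Nothing in the documents shows this: such patients may have started higher, or the dose may have worn off. If they did respond poorly, their carry-over would be small.

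The quoted percentages are open to challenge too. Taken literally, the 3-6 hour duration means that a dose 3 hours earlier may have stopped acting and one 6 hours earlier has, so the true carry-over could be zero. It is also possible that the inclusion wording was meant to cover only the observed dose. As written, however, a patient on repeat doses meets every criterion, and the proforma could not show which patients those were. The flow diagram announced in 7.14 could not be consulted; its stated content is the design, procedures and timing of assessments.

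**Conclusion.** The point holds in conditional form. Entry is open to patients with an earlier dose still acting, T1 is then not an untreated level, and nothing recorded or planned would reveal it. The change from T1 may be biased unevenly across the three readings: towards understatement, most at T4, if the earlier dose is wearing off, and possibly towards overstatement if it has not peaked.

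The sizes in the working are illustrations for affected patients only. They rest on an ONSD effect that tracks plasma half-life, additive doses, and an assumed dose 3 to 6 hours earlier. The average bias scales with the share of affected patients, which the documents do not state. At the 6-hour end it is modest. Neither the net direction nor the size can be fixed from the documents. The stated sample size is unaffected. This is a change that should be made, held with medium confidence, because the missing information is cheap to collect now and may not be recoverable later: 7.13 has the data destroyed after the study.

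**What to change.** 1. **Proforma (Section 19).** Add two fields: whether this is the first mannitol dose of the admission (yes/no), and the time and amount of the last earlier dose.
2. **Section 7.7 or 7.9.** State that T1 is a pre-dose baseline, not necessarily a pre-treatment one.
3. **Section 7.13, main analysis.** Keep the full-set analysis of change after a dose as given. Add an adjustment for a two-level prior-dose variable: none within 6 hours versus a dose within 6 hours. Time since last dose should not be the covariate, because it is undefined for first-dose patients.
4. **Section 7.13, sensitivity analysis.** Prespecify the T2-T4 pattern and the dose correlation in patients with no dose in the previous 6 hours, the protocol's own upper limit for duration of action.
5. **Reporting.** Give the share of patients in each prior-dose category.

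Prescribed treatment is not changed. The cost is two fields and one extra analysis. The downside is that the no-recent-dose subset may be smaller than 35 and so less precise, which is why it is proposed as a sensitivity analysis and not as a replacement for the full set. The fix does not remove regression to the mean from the entry threshold.

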7.13 Plan for Data Management and Statistical Analysis

- Data will be entered by the investigator and resident on duty in the intensive care unit and will be destroyed after the completion of the study, however the results and conclusions will be stored without hampering the subject/ patient's privacy or rights.
- Power of the study is based on the primary outcome which is the change in ONSD following infusion of 20% Mannitol.
- Paired t test, chi square test will be used for data analysis.
- Data will be analysed by using SPSS 20 software version
- The value of $p < 0.05$ will be considered as statistically significant.

7.14 A graphic outline of the study design and procedures using a flow diagram including the timing of assessments.

8. Biases:

Data collection by on duty MD anesthesiology Resident or DM Critical Care Residents will reduce observer and performance bias.

9. Limitation of the study:

- Single centered
- Open label
- No control group

10. Safety considerations:

Regarding the safety concerns during the measurement of optic nerve sheath diameter subjects with ocular injury, glaucoma are being excluded. The acoustic energy used for diagnostic purposes has no described adverse effects. The recent bioeffects and safety report by the American Institute of Ultrasound in Medicine (AIUM) makes no specific mention of the eye. The United States Food and Drug Administration Center for Devices and Radiological Health (US FDA/CDRH) describes an output intensity limit for all eye exposure of 50 mW/cm², recommending the use of a mechanical index (MI) < 0.23, and a thermal index (TI) < 1. The definition of an experienced operator differs, but studies have defined an experienced operator as having performed more than 25 prior transorbital ultrasound examinations.

11. Plan for Supervision and Monitoring:

The research will be continuously supervised by the co-guides [name] [name] and [name] and will be conducted under the guidance of [name].

12. Expected outcome of the Research:

Optic nerve sheath diameter changes are expected to be associated with the administration of 20% Mannitol in patients with raised intracranial pressure. Such an outcome would have various benefits in terms of usefulness of the optic nerve sheath diameter monitoring.

13. Plan for Dissemination of Research:

Research results will be submitted to the Department of Anaesthesiology and Research department, IOM.

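### A paired t test ignores any patient without the later reading, and the plan has no rule for missing readings; if poor early responders are the ones missing, the T4 fall is overstated

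*Combined protocol and SAP*

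**What the plan says.** Section 7.9 names the change in ONSD at T2, T3 and T4 as the primary outcome. By 7.11, these readings come 30, 60 and 120 minutes after the end of a 20-minute infusion, so a patient is followed for about 140 minutes from its start.

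Section 7.6 expects losses: "Assuming a dropout of 10%, the required sample size would be 40". It gives no reasons for them.

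Section 7.13 describes the analysis in one line: "Paired t test, chi square test will be used for data analysis". It has no rule for a missing reading, no sensitivity analysis, and no undertaking to report n at each time point. It also says the data will be destroyed once the study is complete.

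Section 7.12 covers patients whose intracranial pressure and ONSD remain high after mannitol: "decision for further treatment will rest upon the treating physician".

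Section 7.7 lists "Decompressive cranial surgery" as an exclusion without a time reference. The two ocular exclusions beside it are worded as baseline or previous conditions.

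The proforma in Section 19 has a field for each reading and its time, but none for why a reading is absent.

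**The concern.** A paired comparison of T1 with T4 needs both readings. A patient seen at T1 and T2 but not at T4 adds nothing to the T4 result, although the T2 value says something about how that patient was responding. If losses occur, the T2, T3 and T4 changes are estimated in different sets of patients.

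This is harmless when a reading is missing for reasons unrelated to response. It is not harmless when patients with little or no early fall are the ones taken away for further treatment, and 7.12 describes a route by which that could happen. The T4 fall would then be too large, and part of any apparent further fall from T2 to T4 would come from who is left. Both the extent and the pattern of change are aims of the study (Sections 4 and 5). There is no control group (Section 9) against which such selection would show.

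**Working it through.** **Inputs.** From 7.6: mean difference 0.24 and SD of differences 0.49 (no unit printed; taken as mm), two-sided alpha 0.05, power 80%, dropout 10%, 40 enrolled. Not in the documents and therefore assumed: who leaves, why, and the correlation r between the T2 and T4 changes.

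**1. The plan's own figure.** With effect size 0.49, the printed formula gives (1.96 + 0.84)²/0.49² + 1.96²/2 = 32.65 + 1.92 = 34.57, rounded up to 35. This agrees with "The sample size required would be 35". Allowing for dropout, 35/0.9 = 38.9, so 39; the plan enrols 40. The sample size is not the problem. Ten per cent of 40 is 4 patients.

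**2. Simple mixture.** Let q be the share missing at T4, m their mean fall, and 0.24 the mean fall over all patients. Then the completers' mean is (0.24 − q·m)/(1 − q). With q = 0.10:

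| Leavers' mean fall m | Completers' T4 fall | Error |
|---|---|---|
| −0.24 (a rise) | 0.264/0.9 = 0.293 | +22% |
| 0 | 0.240/0.9 = 0.267 | +11% |
| 0.24 (unrelated to response) | 0.216/0.9 = 0.240 | none |
| 0.48 (good responders leave) | 0.192/0.9 = 0.213 | −11% |

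With m = 0, the error is +5% at q = 0.05 and +25% at q = 0.20.

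**3. Loss driven by the T2 response.** Assume a flat true profile (0.24 at both T2 and T4), SD 0.49, and that exactly the 4 of 40 with the least fall at T2 leave before T4, with their T2 readings kept. The large-sample shift in the completers' T4 mean is r × 0.49 × 0.1755/0.9, where 0.1755 is the normal density at the 10% point:
- r = 0.5: 0.048
- r = 0.8: 0.076

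Simulation at n = 40 (20,000 runs) gives completer T4 falls of 0.286 and 0.313. The errors are 0.046/0.24 = 19% and 0.073/0.24 = 30%. T2, measured in all 40, stays at 0.24, so a further fall of 0.05 to 0.07 appears where none exists. In a milder version, where leaving correlates only 0.5 with the T2 change, the T4 fall is 0.263 (r = 0.5) to 0.276 (r = 0.8), or +10% to +15%.

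**4. What using the T2 readings recovers.** In step 3, regressing T4 on T2 and averaging over all 40 patients returns 0.24. This follows from the set-up, because loss was made to depend on T2 alone. If leaving depends on the unseen T4 value, the correction is incomplete. If exactly the worst 10% at T4 left, completers would show 0.336 (+40%).

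**5. What a zero-change analysis does.** Giving the leavers zero change at T4 in step 3 yields 0.9 × 0.286 = 0.257 and 0.9 × 0.313 = 0.282. Both lie nearer 0.24 than the completer figures but are still too large, because the leavers' implied mean there is a rise: (0.24 − 0.257)/0.1 = −0.17 and (0.24 − 0.282)/0.1 = −0.42. If leaving is unrelated to response, the same analysis gives 0.9 × 0.24 = 0.216, which is too small. It is a sensitivity analysis, not a replacement estimate.

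**The case against.** The strongest reply is that nothing shows that losses will depend on response. The 10% in 7.6 is a planning allowance without reasons; unreadable scans or an unavailable operator would fit it as well. Section 7.12 leaves further treatment to the physician but does not say that such patients stop being measured. The window is only about 140 minutes. This stands, and it is why the overstatement can only be conditional.

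A reader might also infer from 7.7 that a patient decompressed after T1 is removed along with readings already taken. The documents do not support that. The project summary (Section 2) records data after eligibility has been met, 7.11 settles the ONSD criterion for inclusion at the baseline measurement, and no section removes an enrolled patient. Nor would such removal create a false further fall. Dropping the same four patients entirely gives a T2 fall of 0.33 and a T4 fall of 0.29 to 0.31, an apparent rebound. The missing time reference is a matter of wording.

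The bias in the extreme case, 0.05 to 0.07, is below one standard error of the completers' mean (0.49/√36 = 0.08). That is true, but a bias is not averaged out like sampling error. With no true change at T4 and 4 of 40 lost, the two-sided rejection rate at the 5% level is 4.7% if leaving is unrelated to the T4 change, 9.1% if the two correlate 0.5, and 27% if exactly the worst four leave.

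Finally, n at each time can be counted from the proforma, and the flow diagram is not visible in the text reviewed and may show participant flow. The reason for a missing reading still has no field on the proforma and may not be recoverable once the data are destroyed.

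**Conclusion.** The gap is real: dropout is expected, the primary outcome spans three later times, and the stated test ignores patients without the reading while the plan says nothing about missing values. That the T4 fall will be overstated is not established.

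The overstatement is 19% to 30% (0.29 to 0.31 against 0.24) if exactly the four least-falling patients at T2 leave. It is about 11% if the 10% who leave had no fall at T4, zero if leaving is unrelated to response, and reversed if good responders leave. These figures rest on the plan's mean and SD; step 3 also assumes a flat profile and values of r that the documents do not give. The point is worth acting on because a better analysis of the same data costs almost nothing, not because the primary result is shown to be biased.

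**What to change.** **Section 7.13.** Replace the separate paired t tests on ONSD by one repeated-measures mixed model on T1 to T4, with time as a categorical factor, using every patient with T1 and at least one later reading. The changes at T2, T3 and T4 are contrasts with T1. SPSS 20, the software already named, can fit it. Report n at each time point.

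**Sensitivity analysis.** Repeat the T4 result with zero change assigned to patients who left for surgery or died. This is needed because the mixed model does not remove bias when leaving depends on the unseen T4 value. Since zero change is not a worst case (step 5), a second run assigning a rise would show how far the conclusion holds.

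**Proforma.** Add one line for the time and reason of any missing reading.

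**Section 7.7 (minor clarification).** State that the decompressive-surgery exclusion is applied at enrolment and that readings already taken are kept.

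The cost is some wording, one proforma line and slightly more analysis work, with no extra patients or measurements. The downside is that the T4 fall may look smaller.
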